Cognitive Strategies: Participants will work with the coach to identify whether perfectionism, pessimism, and all-or-none thinking apply to them and if yes, identify strategies to counter negative thinking through the use of thought stopping and/or positive statements. Likewise, the influence of emotions on eating will be discussed. Attention will be given to motivational issues and relapse prevention. We will use a relapse prevention model to instruct participants to reframe inappropriate eating episodes as temporary slips. Participants will have the option of bringing significant others to in-person sessions by obtaining prior permission from the coach. Participants will also learn how to shop economically by using coupons, frozen vegetables, frequenting farmer's markets and buying foods in bulk when and where practical. Cooking demos demonstrating make-overs of meals with anti-inflammatory compounds such as spices will be provided.

Training of Coaches: Coaches will receive on-site training on the delivery of the comparison and intervention materials and motivational interviewing from [name] (92).

Training will cover the content and delivery of the four in-person and telephone participant contacts. The nutrition coach will target nutrition intervention activities, while the general health coach will deliver the comparison activities focussed on general health-related topics.

Evaluation of the Protocol: We will evaluate the clinic visit protocol and the intervention sessions in the first month and every six months for standardized delivery.

Retention Plan: To maximize retention, the study will provide incentives for data collection activities after randomization. Participants will receive \$20 compensation for each of four completed clinic-based assessments (Baseline, 9 month, 18 month, 27 months) and \$80 for each battery of completed one-week measurement bursts (cognitive test and diet assessment). Participants will also receive a \$5 bonus for completing 80% of daily assessments and an additional \$10 for completing 90% of all assessments.

Data Management for this study will be overseen by [name] and her team, similar to that used in the ESCAPE study. Drs. [name] & [name] will be responsible for data collection and quality control related to cognitive function tasks and ambulatory assessments captured on the smartphone. Dietary data will be downloaded from the NCI ASA 24 web-site and all data will be compiled by the data analyst at Einstein. Data collected using conventional paper and pencil methods for other study instruments are entered by the study coordinators through the relational data base structured specially for this study. The study database system tracks enrollment, participant flow, clinic evaluations, number of follow-up evaluations, and deaths and dropouts in real-time. It also includes summary reports of assessments and interventions longitudinally across bursts. This system includes procedures for documenting the creation and distribution of data sets for specific analyses, and archiving of each data set according to purpose and date of creation. Biospecimens are initially maintained in the Einstein Clinical & Translational Service Award (CTSA) lab, the Biomarker Analytic Research Core (BARC) and shipped to Advanced Research & Diagnostic Lab (ARDL) *at University of Minnesota for analysis*. Laboratory results from outside labs will be electronically transferred, and will undergo quality control checks. Cleaned data will be uploaded through a secure transfer system using the HIPPA compliant Box system and uploaded to the main database. Data will be maintained in a secure environment and subject data will be protected from unauthorized access. The study staff will prioritize protection of the subject privacy, and ensure that access is only given to authorized investigators without compromising a subject's right to privacy. The data server and all computers feeding into it are connected by a local area network (LAN) that is not connected to the Internet. The LAN is a stand-alone network of password protected computers with no connection to any other computers within or outside the institution, which decreases security threats from viruses and virtually eliminates the threat of external "hacking." The computerized data collected will be subjected to SSL 256-bit encryption. There is a similar server at PSU where encrypted ambulatory data are stored. Only encrypted data are transmitted from the ambulatory data collection devices to the servers and from server to server. The servers have been granted an SSL certificate verified by InCommon. This encryption protects participants should the data be intercepted as it is transmitted to the servers. In the unlikely event that interception occurs, the data could not be decoded without the unique encryption key that is held by investigators at both Einstein and PSU. The servers are housed in secure offices at Einstein and PSU and can only be accessed by trained administrators. When data are to be uploaded for access to outside investigators for

analysis, they are de-identified and transferred to an external hard drive and brought to a secure computer with Internet/FTP access.

When the COVID-19 pandemic occurred, participants, investigators and staff were unable to travel into the Einstein clinic facilities. Remote administration of the study protocol put into place. The established LAN system could not be used since access to the clinic site where the physical server, workstations and data reside was not possible. Therefore, the local server environment was temporarily converted to a web-based environment so participant records and data were accessible to authorized personnel via the Internet. The virtual server is protected via a multi-layered encrypted firewall utilizing IP filtering, Windows login security and SQL server authentication. Real time network intrusion software, anti-malware and anti-virus programs run concurrently. No users have the ability to export or download any data. Once the study is able to operate from the clinic site, data collection will return to the original setup.

All of the databases and data entry programs are stored on a dedicated server and maintained by [name], the highly experienced data manager. Multiple automated back-up procedures are implemented nightly to store copies of data and programs at both on- and off-site locations. Data sets are frozen on a semi-annual basis. Specific codebooks are generated for each frozen dataset to document contents, frequencies of included variables, documentation of editing and cleaning procedures, and code used to create calculated variables. Potentially identifiable data will be sent to Kaiser Permanente Washington Research Institute for statistical analyses using Montefiorebox and de-identified data to the University of Minnesota for biospecimen laboratory analyses.

Adaptations to the Pandemic

Beginning with the Covid-19 pandemic on March 13, 2020 all group intervention and comparison sessions were conducted on Zoom. Before the start of the Covid-19 pandemic, in-clinic measures were obtained during site visits that occurred prior to a 2-day baseline “Run-in” period (Run-in Visit), a 7-day Baseline measurement burst (Baseline Visit), 9-, 18-, and 27-month measurement bursts (Follow-up Visits). Beginning with the pandemic all cognitive assessments were conducted online via Zoom except for the NIH Toolbox which was discontinued. We resumed biospecimen collection and anthropometry in-person starting July 16, 2020, after a four month hiatus due to the pandemic.

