the combinations present in the study array by pressing SAME or DIFFERENT buttons located at the bottom of the screen. Test array stimuli remained on the screen until response. Each trial had a 50% chance of being a SAME/DIFFERENT trial. Participants completed 6 trials per assessment (~45 seconds per assessment). The primary outcome for Color Shapes is corrected recognition rate (Hit-rate minus False-alarm rate).

The Shopping List task is a delayed recognition task where participants are asked to determine whether shopping list item-price combinations presented during a retrieval phase match the combinations judged during a price judgment phase of the task. The Shopping List task began with a price judgment phase where participants made subjective judgments of prices (in US dollars and cents) presented alongside hypothetical shopping list items (e.g. ‘bananas’). Participants made 10 subjective price judgments in total during the price judgment phase by pressing “YES” or “NO” buttons in response to the question “is this a good price for [shopping item]” (see Figure 3D). Price judgment phase stimuli were presented for 3000ms each, with an inter-stimulus interval of 1000ms between items. Immediately following the price judgment phase, the retrieval phase began, involving 10 forced-choice recognition trials. Each recognition trial presented one of the shopping list items judged during the price judgment phase accompanied by two prices. One price always matched the price judged during the price judgment phase. The other, non-target price values were always within 9USD of the correct, target price. Both prices were always below 10USD. The order of shopping list item tested during the retrieval phase was randomized with respect to the price judgment phase presentation order. Retrieval phase trials were presented until response. The Shopping List task lasted approximately 60 seconds per assessment. The primary outcome for Shopping List was proportion correct responses during the retrieval phase.

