**Multicultural Healthy Diet to Reduce Cognitive Decline & Alzheimer's Disease Risk
Statistical Analysis Plan 05/05/2018
(version date 9/7/2023)**

Introduction

This document includes a brief description of the study design, objectives, and outcomes, and then describes the analysis plan for the study outcomes at the end of the study. There will be no interim analyses of efficacy outcomes because this is a low risk study of a pilot clinical trial of short duration and important end-points such as sustainability and timing of effects may not be observed if the trial is stopped early, we will not perform interim efficacy analyses. The study team, along with the DSMB, will monitor for safety and quality of conduct throughout the study.

Design Overview

This study is a two-arm randomized controlled clinical trial with an 18-month intervention period. Assessment visits cover a 27-month period (run-in, baseline, months 9 & 18 and 27) at the Aging Research Center (Van Etten Building) at the Albert Einstein College of Medicine (Einstein).

Objectives

To investigate whether consuming the Multicultural Healthy Diet (MHD) can be adapted for a multicultural middle aged (40-65 yr) middle income cohort in Bronx, New York and whether it improves cognition compared to consuming a usual diet.

Outcomes

Primary Outcomes

The primary outcome is a global composite cognition score assessed at 9 months post baseline. The primary outcome will be calculated as a z-score composite measure of three ambulatory cognitive tasks relating to three cognitive domains: visuospatial memory (Grid Memory task), processing speed (Symbol Search task) and a dimension of short-term associative memory binding shown to be sensitive to the early Alzheimer disease neuropathology (Color Shapes task). The global composite score for each measurement burst (baseline, 9months, etc) will be an average of three domain-specific Z-scores based on the within person average response on that domain from up to 35 sessions within a given measurement burst.

Secondary Outcomes

The secondary outcomes relate study arm to dietary intake based on self-report and biomarker measures of intake at 9 months post baseline. In addition, our secondary outcomes will consist of examining dietary effects on each of the three individual tasks (Symbol Search, Grid Memory,

Color Shapes) to determine whether observed intervention effects are attributable to specific cognitive domains.

Randomization

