Randomization occurs after the baseline visit and body measurements when participants are judged to be eligible to proceed to study activities. Stratified permuted block randomization with variable block sizes will be used to randomize participants to one of the two study arms in a 1:1 ratio. Randomization will be stratified on sex, age (<53 yr, 53-65 yr), and education level (no more than high school or equivalent, more than high school), for a total of 8 stratification factors.

Statistical Analysis Plan

Analysis of the Primary Outcome

The primary outcome is a global composite cognition score assessed at 9 months post baseline. The primary outcome will be calculated as a Z-score composite measure of three ambulatory cognitive tasks, each administered up to 35 times, during each measurement burst: Symbol Search, Grid Memory, and Color Shapes. For a given cognitive task (“domain”), an outcome score is calculated for each of up to 35 sessions which are administered over a 1-week measurement burst, approximately 5 sessions per day (administered throughout the day in 5 target ~2 hour windows). For each Burst, and each of the 3 domains, the assigned Z-score is derived from their burst-average response for that domain, and then the three domain burst-average Z-scores are averaged for that Burst to create the primary composite outcome. Note that the Symbol Search and Dot Memory Z-scores **must be multiplied by -1** before creating the composite score because lower scores are better for these tasks. Thus, an increase in the composite score represents better cognitive performance.

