At least 50% (18 out of 35) of the scheduled sessions must be completed for each task in order for a given measurement burst to be considered valid. These 35 scores may take longer than 7 days to accumulate but must be taken without 2-week or larger gap between sessions to be included in the analysis. Each burst has a recorded burst start date; sessions recorded prior to this start date are considered part of the pre-burst training and will be discarded. The first day of the Burst 2 measurement should be inside the visit window (i.e., at least one session no earlier than 3 months and no later than 6 months than the 9-month randomization anniversary) for the Burst 2 measurement to be valid and included in the primary analysis. The domain Z-score is computed using the mean and SD for an individual session, estimated from the baseline (Burst 1) distribution and the measurement burst for an individual i at Burst j is the average task scores across the multiple sessions (up to 35) within that burst. The domain Z-score with fewer than 18 valid sessions will be treated as missing and multiply imputed for the primary analysis, which will be an intent-to-treat analysis. The details are as follows.

The mean and SD are calculated for each domain separately from the baseline measurement (Burst 1). For a given domain, let Y_{i1j}^d be the Burst 1 outcome score from domain d , $d=1,2,3$;

person i , $i=1, \dots, n$; and session $k=1, \dots, m_{i1}$, where m_{i1} is the number of successfully completed sessions at baseline for person i (which may vary by domain d), then:

$$\mu^d = \sum_i \bar{Y}_{i1}^d / n; \bar{Y}_{i1}^d = \sum_j (Y_{i1k}^d) / m_{i1}; SD^d = \sqrt{(\sum_i (\bar{Y}_{i1}^d - \bar{Y}_{1.})^2 / (n-1))}.$$

Then for a given measurement burst $j=1, 2, 3, 4$: where $j=1$ represents baseline and $j=2-4$ represents months 9, 18, and 27, respectively; the domain Z-score for subject i and Burst j is denoted by Z_{ij}^d is calculated from Y_{ijk}^d as:

$$Z_{ij}^d = (Y_{ijk}^d - \mu^d) / SD^d.$$

The three primary tasks (variable names) are:

- Z^1 =Symbol search (SYMBOL_SEARCH.median.RT.accurate_trials)
- Z^2 = Grid Memory (DOT_MEMORY.sum.error.distance.overall)
- o Z^3 = Color Shapes (COLOR_SHAPES.CorRec.rate)

The global assessment score for person i at Burst j is calculated as the average of the three domain average Z score, with Z^1 and Z^2 multiplied by negative 1 so increase is improvement:

$$Z_{ij} = (-Z_{ij}^1 - Z_{ij}^2 + Z_{ij}^3) / 3.$$

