where b_{ij} is the person level effect (random intercept term) for participant i and Burst j , and e_{ijk} is the residual error term assumed to be mean 0, independent across time and individuals and approximately normally distributed. In this model, response Y_{ijk}^d is modeled as a function of the overall baseline level and the term β_4 summarizes the potential treatment effect on the change over time. Models will be further adjusted for age, gender, APOE4 allele, race, and ethnicity in supportive analyses. The difference in time and underlying cognitive function within a burst is assumed negligible, thus the time and season variables in these models will be determined by the first day of the Burst.

The Color Shapes task has only 7 possible values, so a similar generalized estimating equation (GEE) approach will be taken using the Poisson mean model and robust sandwich variance for the number of incorrect responses (0-6).

Our secondary outcomes also include between arm comparisons of MHD-related dietary intake based on self-report and biomarker measures of intake at 9 months post baseline. Outcome models of between-arm differences in dietary intakes indicative of the MHD as measured by nutritional biomarkers, and self-report at Burst 2 will be conducted in a similar manner to the models specified above for the primary cognitive outcomes: namely, ANCOVA models that adjust for the baseline level, Arm and stratification factors will be fit. Tocopherols and carotenoids plasma biomarkers will be additionally adjusted for cholesterol variables per Gross et al (2003). Longitudinal models considering ASA24 data across the 4 bursts will be fit using similar mixed effects models, simplified to analyze only the Burst level average for the ASA24 dietary intakes (no repeated measures within a burst). Analyses will generally be complete case

analyses for the dietary variables. Energy adjustment will be considered where appropriate. Sensitivity analyses with additional adjustment variables associated with missing, as well as exploratory analyses that examine potentially differences in intervention effect by gender, race, ethnicity and age, will also be considered.

The plasma biomarkers include: total folate, alpha and gamma tocopherol, carotenoids (alpha carotene, beta carotene, zeaxanthin+lutein, beta cryptoxanthin, and vitamin B12), lycopene, and fatty acid profile. Serum sodium is an additional secondary outcome, indicative of hydration.

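### If Color Shapes trial types are drawn independently, about 3% of sessions have no score and the primary composite carries avoidable noise; pooling trials over the burst would remove both problems

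*Protocol*

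**What the plan says.** Protocol Section 3 (Ambulatory Cognitive Assessment Procedures) describes the task: "Participants completed 6 trials per assessment (~45 seconds per assessment"), and "Each trial had a 50% chance of being a SAME/DIFFERENT trial". It defines the score: "The primary outcome for Color Shapes is corrected recognition rate (Hit-rate minus False-alarm rate"). It mentions no fixed split of trial types within a session.

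The SAP (Analysis of the Primary Outcome) sets the level of scoring: "an outcome score is calculated for each of up to 35 sessions", and these scores are averaged within the burst. The variable entering the composite is "COLOR_SHAPES.CorRec.rate", with weight one third. A burst needs 18 of 35 sessions per task. The SAP states this rule first in terms of sessions completed and later in terms of valid sessions. A domain score below 18 is set to missing and multiply imputed.

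For the secondary longitudinal model (Analysis of Secondary Outcomes), the SAP uses a different Color Shapes outcome, the number of incorrect responses from 0 to 6.

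Neither document says what score a session gets when all six trials are of one type. Neither weights sessions by their split or pools trials over a burst.

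**The concern.** A hit rate needs at least one trial of one type, and a false-alarm rate at least one of the other. With six random trials, some sessions lack one type and have no score. Others estimate one rate from a single trial, yet count as much in the burst average as a session split three and three.

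Three things are at stake:

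- **Specification.** Two analysts could build different primary outcomes from the same data, one dropping unscorable sessions and the other filling the missing rate with zero.
- **The 18-session rule.** A completed but unscorable session falls between the two wordings of the rule.
- **Precision.** The primary model is an ANCOVA on the baseline burst score, so measurement error in the burst scores feeds its residual variance. Protocol Section 2.2.3 gives reliability of averaged scores for Grid Memory and Symbol Search (0.97 and 0.98), but none for Color Shapes.

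**Working it through.** **The plan's own figures.** Protocol Section 9.2 gives 80% power for 0.35 SD with 125 per arm. Two-sided alpha of 0.05 is assumed, as the documents state none.

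- Φ(0.35 × √(125/2) − 1.96) = Φ(0.807) = 79.0%.
- With 143 in total: Φ(0.35 × √(71.5/2) − 1.96) = 55.3%, against 54% stated.
- The absolute differences follow from 0.35 × √(2(1 − ρ)): 0.157, 0.192 and 0.350 for ρ = 0.90, 0.85 and 0.5.

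The plan's power figures are therefore reproduced to within about 1.5 points.

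**Split of trial types.** If draws are independent, the number of trials of one type is Binomial(6, 0.5).

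| Split | Probability |
|---|---|
| 6:0 or 0:6 (no score) | 2/64 = 3.1% |
| 5:1 or 1:5 | 12/64 = 18.75% |
| 4:2 or 2:4 | 30/64 = 46.9% |
| 3:3 | 20/64 = 31.25% |

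A full burst has on average 35 × 2/64 = 1.09 unscorable sessions. The chance of at least one is 1 − (62/64)^35 = 67%.

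**Noise.** With hit rate h, false-alarm rate f and n trials of the first type, the trial-sampling variance of a session score is h(1 − h)/n + f(1 − f)/(6 − n).

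- Mean of 1/n over scorable sessions: (6/1 + 15/2 + 20/3 + 15/4 + 6/5)/62 = 0.405. A 3:3 split gives 0.333, so the ratio per scorable session is 1.215.
- Counting the lost sessions: (0.405/0.96875)/0.333 = 1.25 for the burst mean. The ratio does not depend on h or f. A simulation against pooled scoring gave 1.26.
- Example with assumed h = 0.85, f = 0.20 and 35 sessions: standard error 0.0586 as planned, 0.0525 pooled, 0.0523 with a fixed 3:3 split.

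The ratio covers trial sampling only. If true ability also varies between sessions, simulation gives 1.20 at an assumed session SD of 0.2 and 1.15 at 0.3.

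**Bias.** If unscorable sessions are dropped, the simulated mean is 0.650 against a true 0.65. If the missing rate is filled with zero, the expectation is (62/64)(h − f) + h/64 − f/64 = (63/64)(h − f) = 0.640, in either arm alike.

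**The 18-session rule.** Chance of fewer than 18 scorable sessions, by number completed:

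- 18 completed: 1 − (62/64)^18 = 44%
- 19 completed: 12%
- 20 completed: 2%
- 22 completed: 0.05%

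At 28 sessions, the 80% compliance expected from Protocol Section 2.2.3, it is effectively zero.

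**Effect on the composite.** This part needs inputs that the documents do not give.

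- Two-burst simulation, assuming mean rates of 0.8 and 0.3, between-person SD 0.12–0.25, true burst-to-burst correlation 0.93–0.97 and 18–35 sessions: pooling lowers the Color Shapes ANCOVA residual variance by 9–17%. If the three tasks contribute similar, nearly uncorrelated residual variance, a third of that is 3–6% for the composite.
- Power at 125 per arm: Φ(0.35/√0.97 × 7.906 − 1.96) = 80.2% and Φ(0.35/√0.94 × 7.906 − 1.96) = 81.4%, where 7.906 = √(125/2).
- Wider grid for the change score, with between-person SD 0.10–0.25, rates 0.85/0.20 or 0.75/0.30, inter-task correlation 0.3–0.5 and 28–35 sessions: current scoring inflates the composite's change variance by about 2–18% at ρ = 0.90, but only 0.3–3% at ρ = 0.5.

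**The case against.** The strongest objection is that a 50% chance per trial does not establish independence. A shuffled list of three SAME and three DIFFERENT trials also gives each trial a 50% chance. Under that design every session is scorable and there is no excess noise. This stands as a condition on the finding. Random draws are the natural reading of the protocol, but the sponsor must confirm it.

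It is also fair that averaging session scores is one uniform, prespecified rule for all three tasks, and that the gain on the composite depends on assumed inputs. A change now also comes late: Protocol Section 3 reports 260 participants already at the second visit.

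Three stronger readings are tempting, and the documents do not support them:

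- **That the SAP misreads the scale of the endpoint.** It says "The Color Shapes task has only 7 possible values", whereas hit rate minus false-alarm rate has 21 possible session values under random splits. But the same SAP sentence ties the seven values to the error count from 0 to 6, so there is no misreading.
- **That many bursts would be lost under the 18-session rule.** The 44% applies only at exactly 18 completed sessions. Loss also follows only if the later wording of the rule (valid sessions) governs.
- **That the arm contrast is biased.** Dropping unscorable sessions leaves the average unbiased, and the scoring treats both arms alike.

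**Conclusion.** The point holds as a cheap gain in precision and a gap in specification. It does not threaten the trial's validity. Given independent draws, the 3.1% of unscorable sessions, the 19% with a rate resting on one trial, and the 1.25 ratio of trial-sampling variance follow exactly from the protocol's task description. Uneven splits cause most of the excess noise (21.5%); lost sessions add only about 3%.

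The consequence for the primary analysis is modest and less certain. A rise in power from about 79% to 80–81% rests on assumed Color Shapes rates, between-person spread and high burst-to-burst correlation. Section 9.2 cites about 0.90 from an earlier study but also considers 0.5, where the gain nearly vanishes. If a 3:3 split was programmed, pooled and session-averaged scores are identical for complete sessions, so the change does no harm.

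**What to change.** First confirm from the task software how trial types were allocated and what value was stored for a session with only one type. Then, in the SAP:

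1. Under Analysis of the Primary Outcome, define the Color Shapes burst score as total hits divided by hit-eligible trials, minus total false alarms divided by false-alarm-eligible trials, over all completed sessions in the burst. Take the Color Shapes mean and SD from these pooled Burst 1 scores.
2. Count every completed six-trial session towards the 18, whatever its split.
3. Under Imputation Models for the Ambulatory Cognitive Scores, use the same pooled scoring for the run-in and first-10-session Color Shapes variables.
4. Keep the session-averaged score as a sensitivity analysis, with a stated rule for one-type sessions.

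The cost is a recode and a dated, documented change to one component of the primary endpoint, made without reference to arm. No new data are needed if the trial-type counts behind the session rates were stored, which should be checked first.

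The SAP's secondary model for the error count needs no correction on this account.
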